12-lead EC ^f G	○	○ ^g			○		○	○ ^e	
Clinical laboratory tests	○	○ ^g			○		○	○ ^e	
Pregnancy test ^h	○	○ ^g			○		○	○ ^e	
IGA	○	○	○	○	○	○	○		
EASI		○	○	○	○	○	○		
VAS for pruritus		○	○	○	○	○	○		
VRS for pruritus		○ ⁱ	↔	○					
DLQI		○	○	○	○	○	○		
POEM		○	○	○	○	○	○		

<Schedule of Observations/Examinations/Evaluations, Continued>

Evaluation	Screening period (2–30 days)	Assessment period (8 weeks)							Post-treatment observation period (2 weeks)
		Baseline examination	Week 1 examination ^a	Week 2 examination ^b	Week 4 examination ^b	Week 6 examination ^b	Week 8 examination ^b	Withdrawal examination	
Affected BSA	○	○	○	○	○	○	○	○	
Treatment area		○	○	○	○	○		○	
Blood sampling for plasma drug concentration measurement			○ ^J		○ ^J		○ ^K		
Administration diary		○ ^I	←	→			○		
Severity of AD		○							
Status of IMP administration			○	○	○	○	○		
Prescription and collection of IMP		○ ^m	○ ⁿ	○	○	○	○ ^o	○ ⁿ	
Adverse events		←	→						
Concomitant medications and therapies		←	→						
Patch test ^p		←	→						

AD = atopic dermatitis; DLQI = Dermatology Life Quality Index; EASI = Eczema Area and Severity Index; IGA = Investigator's Global Assessment; POEM = Patient-Oriented Eczema Measure; VAS = Visual Analogue Scale; VRS = Verbal Rating Scale.

^a Acceptable window of ± 2 days

^b Acceptable window of ± 3 days

^c Acceptable window of ± 7 days

^d Withdrawal examination should be conducted as much as possible.

^e May be conducted, as necessary.

^f Should be conducted prior to blood sampling, as much as possible.

^g Results of the screening examination should be used when the baseline examination is planned within 7 days of the screening examination.

^h Should be conducted only for women with childbearing potential.

ⁱ Should be evaluated during the baseline examination, 4 ± 2 hours, 8 ± 2 hours, and 12 ± 2 hours (if possible) after the first IMP administration, and then twice daily from the next day (before IMP administration in the morning and at night) until the morning of the Week 1 examination (without IMP application) (up to the morning of Day 7 at the latest).

^j On the day of blood sampling, the first IMP application should not be done until after blood sampling when visiting the trial site.

^k On the day of examination, the subjects should not administer the IMP.

^l The subjects should keep a diary every day from the baseline examination to the Week 8 examination (withdrawal examination).

^m Only IMP prescription.

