7.1.4 Baseline Examination (2-30 Days After the Screening Examination)

The investigator or subinvestigator will perform the following examinations, observations, and evaluations, and record the results in the source document and CRF.

- Physical examination
- Vital signs (including body weight)
- Clinical laboratory tests (The screening examination results can be used within 7 days of the screening examination.)

- Pregnancy test (only for women of childbearing potential. The screening examination results can be used within 7 days of the screening examination.)
- 12-lead ECG (The screening examination results can be used within 7 days of the screening examination.)
- IGA
- EASI
- VAS for pruritus
- VRS for pruritus
- DLQI
- POEM
- Affected BSA
- Blood sampling for plasma drug concentration (to be conducted at specific trial sites)
- Severity of AD
- Adverse events
- Concomitant medications and therapies

The investigator or subinvestigator will select subjects who meet the inclusion criteria and do not meet any of the exclusion criteria based on results of the screening and baseline examinations. Also, the investigator or subinvestigator will record the results of the subject's eligibility on the list of screened subjects and the list of enrolled subjects.

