7.2.1.3 Visual Analogue Scale (VAS) for Pruritus

The investigator or subinvestigator will evaluate the level of pruritus based on VAS⁷. The subjects will mark the point of pruritus intensity during the last 24 hours on the line of a 100-mm VAS sheet (Appendix 2) between the left end (no pruritus) and the right end (very severe pruritus). The investigator or subinvestigator will record the length from the left end to the mark (integer value with mm as unit) in the medical record and CRF. The VAS sheet will be kept as the source document.

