7.2.1.4 Verbal Rating Scale (VRS) for Pruritus

The investigator or subinvestigator will evaluate the pruritus intensity based on VRS⁷.

The subjects will evaluate the pruritus intensity according to the following criteria.

The subjects will record the level of pruritus, and the time and date of evaluation in a pruritus diary.

0: None

1: Mild

2: Moderate

3: Severe

The investigator or subinvestigator will record details of the pruritus diary in the CRF. The pruritus diary will be kept as the source document.

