### **9.2.3 Changes From Baseline in Overall EASI Score and EASI Symptom Scores at Week 1, Week 4, and Week 8**

Based on the OC data set, the change from baseline in EASI score (at Week 1, Week 2, Week 4, Week 6, and Week 8; If the timing of discontinuation falls within the allowable window of a timepoint, the data at discontinuation will be included as the data for the timepoint) will be analyzed using the MMRM analysis with treatment (0.3% or 1% OPA-15406 group, and vehicle group), timepoint, and interaction between treatment and

timepoint as factors and baseline EASI score as a covariate. An unstructured covariance matrix will be used to model the within-subject errors and Kenward-Roger method will be used to calculate the standard error of fixed-effects and the degree of freedom. If the MMRM procedure fails to converge under unstructured covariance structure, the following structure will be used in the order of 1) heterogeneous toeplitz, 2) heterogeneous autoregressive of order 1, 3) heterogeneous compound symmetry, and the first (co)variance structure converging to the best fit will be used.

The least square mean of each treatment group will be calculated by timepoint. For overall EASI score, the least square mean and the standard error will be plotted by timepoint for each treatment group. The difference in the least square mean between the vehicle group and each OPA-15406 group, and the two-sided 95% confidence interval and p-value will be calculated at Week 1, Week 4, and Week 8 (as well as at Week 2 and Week 6). Based on the OC and LOCF data sets, ANCOVA model with treatment (0.3% or 1% OPA-15406 group, and vehicle group) as a factor and baseline EASI score as a covariate will be applied to the change from baseline up to each timepoint. The least square mean in each treatment group will be calculated by timepoint. The difference in the least square mean between the vehicle group and each OPA-15406 group, and the two-sided 95% confidence interval and p-value will be calculated at Week 1, Week 4, and Week 8 (as well as at Week 2 and Week 6). Based on the OC and LOCF data sets, measured values and changes from baseline in IGA at Week 1, Week 4, and Week 8 (as well as at Week 2 and Week 6) will be summarized by treatment group using descriptive statistics. For the overall EASI score, the mean with standard error of measured values (in the OC and LOCF data sets) will be plotted by timepoint for each treatment group.

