#### **9.2.5 Change From Baseline in VRS for Pruritus up to Day 7**

The change from baseline in VRS for pruritus up to Day 7 will be analyzed in the same manner as that in overall EASI score or each EASI symptom score. Data will be collected

at baseline, 4, 8, and 12 hours after the start of administration, 1 day after the start of administration (morning and night), and thereafter in the same manner up to Day 7 (morning). The same analysis will be performed by the time zone of assessment (morning or evening). Morning or evening will be determined based on the time label entered in the case report form (CRF), not using the timepoints defined in Table 6.4-2, except the baseline, which is irrespective of the time zone of assessment. Data will be collected at baseline, and the timepoints specified above on Day 1 to Day 7.

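### The VRS itch models adjust only for one four-level baseline reading; adding the baseline pruritus VAS already collected would probably gain a little precision at no data cost

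*Protocol*

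**What the plan says.** The footnote to the VRS row of the protocol's schedule fixes the reading times: "Should be evaluated during the baseline examination", then about 4, 8 and (if possible) 12 hours after the first dose, then twice daily to the morning of Day 7 at the latest. Only the first of these precedes treatment. Protocol 7.2.1.4 gives the scale as four levels, 0 (none) to 3 (severe), rated by the subject, and states no recall period: "The subjects will evaluate the pruritus intensity according to the following criteria".

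Protocol 11.3.1.2 analyses VRS change by ANCOVA on treatment and the baseline value. SAP 9.2.5 sends VRS to the same models as EASI. The template in SAP 9.2.3 has treatment, timepoint and their interaction, with "timepoint as factors and baseline EASI score as a covariate". For VRS that means baseline VRS and nothing else. SAP 9.2.5 repeats the analysis separately for morning and evening readings, labelled by time of day "except the baseline, which is irrespective of the time zone of assessment", so one baseline value serves both.

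The baseline examination list in Protocol 7.1.4 also contains "VAS for pruritus". Protocol 7.2.1.3 describes it: "The subjects will mark the point of pruritus intensity during the last 24 hours on the line of a 100-mm VAS sheet". No VRS model uses it. Protocol 11.3.7 and SAP 6.6.1 make p-values for all variables other than the primary one for reference, without multiplicity adjustment.

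**The concern.** A single reading on a four-level scale is a coarse and noisy measure of how much a subject usually itches. Adjusting for it removes only part of the between-subject variation in later VRS scores. The VAS measures the same symptom on a finer scale over a stated 24-hour window, so it may carry information about later itch that the clinic VRS lacks. This applies most clearly to the morning and evening analyses, where the only adjuster is a reading taken at whatever hour the visit fell.

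At stake is the width of the confidence intervals for VRS change at the 16 timepoints in SAP Table 6.4-2 and in the morning and evening analyses. VRS is the only itch measure repeated before the Week 1 visit, and the trial was not sized for it.

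**Working it through.** **The plan's own figure.** The only stated sample size concerns IGA success at Week 4: 20.93% against 2.70%, two-sided 5%, at least 80% power, 54 per group. The exact power of the two-sided Fisher test is 79.1% at 53 and 80.2% at 54 per group, so 54 reproduces. Allowing 10% dropout, 54/0.9 = 60. None of this bears on VRS, for which the documents give no SD, effect size or power.

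**Is the VAS eligible as a covariate?** Protocol 7.1.5 starts dosing only after all baseline examinations are finished. The VAS is therefore a pre-treatment value, and adding it leaves the randomised contrast unbiased and the target mean difference unchanged.

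**Formula.** Let y be a later VRS, b baseline VRS and v baseline VAS. Given treatment and b, the squared partial correlation of v with y is

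r² = (r_yv − r_yb·r_bv)² / [(1 − r_yb²)(1 − r_bv²)].

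Adding v multiplies residual variance by 1 − r² and interval width by √(1 − r²). Sixty per arm then acts like 60/(1 − r²).

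**Assumed correlations** (none is in the documents): r_yb from 0.3 to 0.6, r_yv within 0.1 of r_yb, r_bv from 0.5 to 0.8. Worked case with 0.5, 0.5 and 0.7: (0.5 − 0.35)² / (0.75 × 0.51) = 0.0225/0.3825 = 0.059, so √0.941 = 0.970.

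| r_yb | r_yv | r_bv | r² | Width ratio | 60 acts like |
|---|---|---|---|---|---|
| 0.5 | 0.4 | 0.8 | 0.000 | 1.000 | 60 |
| 0.3 | 0.3 | 0.7 | 0.017 | 0.991 | 61 |
| 0.5 | 0.5 | 0.7 | 0.059 | 0.970 | 64 |
| 0.6 | 0.6 | 0.6 | 0.141 | 0.927 | 70 |
| 0.5 | 0.6 | 0.5 | 0.218 | 0.884 | 77 |

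**Simulation with a latent itch level and a four-level VRS.** What matters is how much of the momentary error in the clinic VRS the VAS shares.

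- Stable itch as 40% to 80% of variance: r² is 0.01 to 0.08 if the VAS carries the whole clinic-moment component, and 0.09 to 0.24 if it carries half.
- Latent SD 1, VRS noise SD 0.6–1.2, VAS noise SD 0.3–0.8, drift SD 0.3–0.6, errors independent: residual-variance ratio 0.76 to 0.92; with other VRS cut-points, 0.73 to 0.91.
- The same noise ranges with the VAS carrying 70% of the baseline VRS error: variance falls 3% to 11%, intervals are 1.4% to 5.7% narrower, and 60 acts like about 62 to 67.
- All of that error shared: ratios as high as 0.995.

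At the extremes, √0.995 = 0.997 (0.3% narrower; 60/0.995 = 60.3) and √0.73 = 0.854 (about 15% narrower; 60/0.73 = 82).

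**In power terms.** A VRS contrast with 80% power under the planned model would have 80.8%, 82.0%, 84.0% or 87.9% at r² of 0.02, 0.05, 0.10 or 0.20.

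**Limit of the check.** These figures are for one follow-up reading at a time, as in the ANCOVA. The template MMRM has one baseline slope and no baseline-by-visit term. A single VAS slope over 16 timepoints cannot gain more than separate slopes would, and that gain was not computed.

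**The case against.** Adjusting each score for its own baseline is the plan's uniform, pre-specified rule, and randomisation makes it valid. Nothing in the documents is contradictory or ambiguous here. One could by the same logic add baseline EASI, POEM or DLQI to every model. VRS is one of nine secondary variables, and no sample size, power claim or decision depends on it.

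Most of this stands: the plan contains no error on this point. The choice of VAS is less arbitrary than the objection suggests, because it measures the same symptom at the same visit over a longer window.

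The objection also rightly blocks some stronger readings. A reader might infer a definite gain of 8% to 24% in residual variance. That range needs VAS and VRS errors to be independent, yet both are the same subject's ratings at one visit, so shared error is plausible and the gain can approach zero. A reader might also take VRS as the only evidence on itch in the first week. It is not: VAS change at Week 1 is a named secondary variable. Finally, time to response in VRS (SAP 9.2.11) uses unadjusted Kaplan–Meier and log-rank methods and would not benefit.

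**Conclusion.** The point holds as an optional efficiency gain. The VRS models leave out a pre-dose measure of the same symptom that is already collected, and probably lose some precision as a result. The loss is real only if the VAS predicts later VRS beyond baseline VRS. The documents cannot settle that, and the contrast between a momentary VRS and a whole-day VAS is partly inferred, since the VRS has no stated recall period.

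Under the assumptions shown, the gain runs from near nil to about 10–15% in interval width (60 per arm acting like about 60 to 80), with a few percent most plausible. It would be wrong to infer that the planned VRS comparisons are biased or invalid: they are randomised comparisons with a pre-specified baseline adjustment. The primary endpoint, its power and its type I error are unaffected.

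**What to change.** Before unblinding, amend SAP 9.2.5 to keep baseline VRS and add baseline pruritus VAS (mm) as a second continuous covariate in the VRS MMRM and ANCOVA, including the morning and evening analyses. Where baseline VAS is missing, impute the overall baseline mean, blind to arm, so that no subject is dropped. List the change and its reason in SAP 13.1. Timing matters because Protocol 11.4 requires analyses changed after unblinding to be reported separately from the planned ones.

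The cost is a sentence of SAP text, one more term in the model code and one degree of freedom out of about 176 (180 subjects less intercept, two treatment terms and baseline VRS). No new data are needed.

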Appendix 1: Diagnostic Criteria for Atopic Dermatitis (Hanifin & Rajka)

Appendix 2: Visual Analogue Scale (VAS) Sheet for Pruritus

Appendix 3: Dermatology Life Quality Index (DLQI)

Appendix 4: Patient-Oriented Eczema Measures (POEM)

Appendix 5: Human Body Drawing

List of Abbreviations and Definition of Terms

List of Abbreviations

Abbreviation	Expansion
AD	Atopic dermatitis
AST	Aspartate aminotransferase
ALT	Alanine aminotransferase
BSA	Body Surface Area
cAMP	Cyclic adenosine 3', 5'-monophosphate
COM	Clinical Operation Manual
DLQI	Dermatology Life Quality Index
EDC	Electronic Data Capture
EASI	Eczema Area and Severity Index
FAS	Full Analysis Set
GOT	Glutamic oxaloacetic transaminase
GPT	Glutamic pyruvic transaminase
ICH	International Conference on Harmonisation of Technical Requirements for Registration of Pharmaceuticals for Human Use
IGA	Investigator's Global Assessment
IUD	Intrauterine Device
IWRS	Interactive Web Response System
LC-MS/MS	Liquid chromatography with tandem mass spectrometry
LOCF	Last Observation Carried Forward
MedDRA	Medical Dictionary for Regulatory Activities
MMRM	Mixed Model Repeated Measure
OC	Observed Case
PDE	Phosphodiesterase
POEM	Patient-Oriented Eczema Measure
QTcF	QT interval as correlated by Fridericia's formula
SS	Safety Set
TEAE	Treatment-emergent Adverse Event
NB-UVB	Narrow-band UVB
VAS	Visual Analogue Scale
VRS	Verbal Rating Scale

Definitions of Terms

Term	Definition
Screen failure	A screen failure is a subject from whom written informed consent was obtained, but to whom an investigational medicinal product was not allocated.
Individual subject trial start date	The day of obtaining the subject's written informed consent
Individual subject trial discontinuation date	The day of discontinuation of a subject who was withdrawn from the trial before the Week 8 examination will be the day of examination 2 weeks after the last IMP administration. For those who missed the examination 2 weeks after the last IMP administration, the day of discontinuation will be the day when the investigator or subinvestigator determined that the subject was to be withdrawn from the trial.
Individual subject trial completion date	For subjects who underwent the Week 8 examination, the day of trial completion will be the day of examination 2 weeks after the last IMP administration.
Individual subject trial period	Period from the day of obtaining the subject's written informed consent to the day of trial discontinuation or completion. Does not include the follow-up period.

List of Pharmacokinetic Parameters

Abbreviation and Term (Unit)		Expansion or Definition
AUC	ng•h/mL	Area under the plasma concentration-time curve
AUC _{8h}	ng•h/mL	Area under the plasma concentration-time curve from time zero to 8 hours
AUC _∞	ng•h/mL	Area under the plasma concentration-time curve from time zero to infinity
C _{max}	ng/mL	Maximum plasma concentration of the drug

1 Introduction (Background Information of the Present Trial)

1.1 Background of Trial Plan

Atopic dermatitis (AD) is defined as “a disease with repeated exacerbations/remissions of which the main lesion is eczema with pruritus, and most patients have atopic predisposition. Atopic predisposition means 1) having a family history/medical history (one or more diseases of bronchial asthma, allergic rhinitis/conjunctivitis, or atopic dermatitis) or 2) predisposition to producing IgE antibody.”² In some patients, atopic dermatitis that occurred in infancy may spontaneously resolve with age. Some patients experience the onset or recurrence of the disease in adulthood, namely, refractory atopic dermatitis in adults.

Diagnostic criteria for the disease were established by Hanifin and Rajka in 1980¹, and in Japan, Guidelines for Management of Atopic Dermatitis was published by the Japanese Dermatological Association². The universally accepted concept of the disease is that AD is chronic eczema accompanied by physiological dysfunction of the skin and inflammation caused by multiple nonspecific stimuli or specific allergens.

The therapeutic strategies of AD are also common in the world. Topical agents such as steroids and calcineurin inhibitors (immunosuppressors) are used for the treatment of inflammation, topical moisturizers and protective agents for skin care to treat abnormal physiological functions, and oral antihistamines and antiallergic agents for pruritus as adjuvant treatment. Elimination of as many aggravating factors as possible has been established by current consensus as a basic therapy for AD. Inflammation can generally be suppressed by topical steroids. However, long-term use of steroids may induce adverse drug reactions (eg, skin atrophy, hairiness); therefore, drugs with long-term safety have been anticipated.

Phosphodiesterase (PDE) 4 is an enzyme that hydrolyzes cyclic adenosine 3', 5'-monophosphate (cAMP) and exists in inflammatory cells, such as macrophages, lymphocytes, and neutrophils³. In AD patients, elevated PDE activity in peripheral blood leukocytes and reduced intracellular cAMP levels are observed. PDE4 inhibitors exert their antiinflammatory activity by increasing intracellular cAMP levels and suppressing production of inflammatory cytokines and chemical mediators. Therefore, PDE4 inhibitors have been considered effective for treatment of atopic dermatitis.

OPA-15406 is a PDE4 inhibitor synthesized by Otsuka Pharmaceutical Co., Ltd. In a mouse chronic contact hypersensitivity model, OPA-15406 ointment demonstrated

its efficacy on dermatitis by improving the symptoms. Therefore, development of OPA-15406 ointment was started with the expectation of efficacy for AD.

Clinical development OPA-15406 has preceded outside Japan, and the phase 2 trial in AD patients (271-12-205) has been completed. In Japan, the phase 1 trial in healthy adult male subjects has been completed. In healthy adult subjects and AD patients, OPA-15406 ointment showed no clinical relevant safety issues but good tolerability. Also, in the phase 2 trial outside Japan, 1% OPA-15406 ointment demonstrated the efficacy on AD. Based on these results, the present trial is designed to assess the efficacy and safety of OPA-15406 ointment in Japanese AD patients. While this trial will be conducted in adult patients (aged 15 years and older), the trial design will be the same as that of the phase 2 trial outside Japan to the extent possible to allow comparability with the foreign trial results.

1.2 Study Results and Trial Rationale

1.2.1 Nonclinical Study Results

OPA-15406 had potent and selective PDE4 inhibitory actions, especially against PDE4B, and its 50% inhibitory concentration was 0.0112 μ M.

Using a mouse chronic contact hypersensitivity model as an animal model of atopic dermatitis, the dose-dependent efficacy of the OPA-15406 ointment (0.03% to 3%) for chronic allergic dermatitis was assessed. Four weeks of topical administration of the OPA-15406 ointment showed dose-dependent efficacy in improving skin thickening at 0.03% to 3%. The effect was inferior to that of betamethasone valerate, a strong steroid, and superior to that of tacrolimus ointment, a calcineurin inhibitor. Four weeks of multiple administrations of 3% OPA-15406 ointment significantly suppressed infiltration of inflammatory cells such as CD3 positive cells, eosinophils, and neutrophils in skin lesions.

Using a mouse scratching-induced chronic dermatitis model, the efficacy of OPA-15406 (1% and 3%) dissolved in a solvent (1:1 mixture of acetone and methanol) was assessed. Six weeks of topical administration of OPA-15406 (1% or 3%) significantly improved the skin symptoms, though no particular effect was observed on the frequency of scratching. The efficacy was superior to that of betamethasone valerate (0.1%) and tacrolimus (0.1%) dissolved in the solvent.

The efficacy of OPA-15406 ointment (3%) was assessed in a mouse acute contact hypersensitivity model. Single administration of the OPA-15406 ointment

(3%) significantly suppressed edema. The efficacy was equivalent to betamethasone valerate (Rinderon[®]-V ointment 0.12%) and tacrolimus ointment (Protopic[®] ointment 0.1%).

OPA-15406 ointment (0.1%, 0.3%, 1%, and 3%) was administered percutaneously to rats at 0.3, 0.9, 3, or 9 mg/kg as a single-dose. C_{max} and AUC of OPA-15406 increased dose-dependently at 0.3 to 3 mg/kg, and reached a plateau at 3 to 9 mg/kg.

Single percutaneous administration of the OPA-15406 1% ointment at 3 mg/kg was performed for abraded skin of male rats. The C_{max} and AUC_{∞} of OPA-15406 in the male rats with abraded skin were 2.0 and 1.6 times that in male rats with intact skin.

With percutaneous administration of ¹⁴C-OPA-15406 1% ointment in rats, the amount of detected OPA-15406 on the skin of the administration site was largest, and the metabolites of MAP-15484, MAP-15485, and MAP-15497 were also detected. OPA-15406, MAP-15484, and MAP-15485 were detected in the plasma of the rats treated percutaneously and subcutaneously with ¹⁴C-OPA-15406 1% ointment.

In a 4-week repeated-dose percutaneous toxicity study in rats, white petrolatum, OPA-15406 ointment 0% (vehicle), 0.1% (1.06 mg/kg for male, 1.25 mg/kg for female), 0.3% (3.27 mg/kg for male, 3.78 mg/kg for female), 1% (11.02 mg/kg for male, 12.74 mg/kg for female), or 3% (33.56 mg/kg for male, 38.56 mg/kg for female) was administered to intact skin (open cutaneous) approximately equivalent to 10% of total body surface area (BSA) once daily. No changes associated with the test substance were observed at the administration sites in any treatment groups. Body weight and/or food consumption were reduced in the male rats treated with 1% and 3% ointments and in female rats treated with 0.1%, 0.3%, and 1% ointments. These changes were reversible or likely to be reversible during the 4-week recovery period. In a 13-week repeated-dose percutaneous toxicity study in rats, white petrolatum, OPA-15406 ointment 0% (vehicle), 0.1% (0.31 mg/kg for males, 0.38 mg/kg for females), 0.3% (0.92 mg/kg for males, 1.13 mg/kg for females), 1% (3.08 mg/kg for males, 3.75 mg/kg for females), or 3% (9.39 mg/kg for males, 11.47 mg/kg for females) was administered to intact skin (open cutaneous) approximately equivalent to 3% of total BSA once daily. No changes associated with the test substance were observed at the administration sites in any treatment groups. Increase in body weight was suppressed in the male and female rats with 3% ointment. The no observed adverse effect dose level of systemic toxicity was estimated to be 1% ointment (3.08 mg/kg) for males and 1% ointment (3.75 mg/kg) for females.

In a 4-week repeated-dose percutaneous toxicity study in rabbits, white petrolatum, OPA-15406 ointment 0% (vehicle), 0.1%, 0.3%, 1%, or 3% was administered to intact skin (open cutaneous) approximately equivalent to 10% of total BSA once daily. The OPA-15406 ointment was classified as weak skin irritation at all concentrations according to the Draize scale for skin irritation.

In a 8-week repeated-dose percutaneous toxicity study in juvenile rats (25 days old at the start of administration), white petrolatum 0% (vehicle), OPA-15406 ointment 0.3% (male: 3.76 mg/kg; female: 4.23 mg/kg), 1% (male: 12.56 mg/kg; female: 14.32 mg/kg), or 3% (male: 38.52 mg/kg; female: 43.83 mg/kg) was administered once daily to intact skin (open cutaneous) approximately equivalent to 10% of total BSA. As a result, no changes associated with the test substance were observed on the administration sites in any of the treatment groups. Although suppressed weight increase and reductions in food intake and grip strength were observed in the female rats with 1% or 3% ointment, these changes were not developmental toxicity and they resolved with washout. Also, there was no difference in the toxicity threshold between adult and juvenile rats. As the profile of OPA-15406 is such that it reaches the CNS and the brain is known to develop after birth, a 10-week repeated-dose percutaneous toxicity study was conducted in neonatal rats (4 days old at the start of administration) with a focus on CNS development, but no influence of OPA-15406 on the function or structure of the CNS was found.

